4.0 STUDY PLAN

4.1 Study Procedures

4.1.1 Study Design

This will be a single arm, non-blinded study of PAE in a small population with BPH to determine if PAE is as effective as medication (non-inferiority) in reducing urinary symptoms due to BPH. After IRB approval of a written informed consent and over approximately a 24 month duration, a total of N=30 subjects will be recruited at 3 sites. Only subjects \geq 40 years will be screened for study recruitment. Clinical procedures and evaluations will consist of a preoperative screening assessment to determine if the potential study subject meets the inclusion and exclusion criteria, enrollment, surgical procedure for prostatic artery embolization (PAE), and follow-up visits at 24 hours, 1 week, 3, 6, & 12 months. An MRI will be performed after the 6-month visit in those patients who underwent embolization to detect a change in prostatic volume and perfusion and to exclude complication.

4.1.2 Study Treatment

Subjects will be given a dose of antibiotics on the day of the procedure (Bactrim 400mg/80mg or Cipro 500 mg if the patient has an allergy to sulfa drugs. Additionally, non-steroidal anti-inflammatory medication will be administered on the day of procedure (500 mg Naproxen). The patients will be given the choice of receiving intravenous anxiolytic and analgesic medication during procedure or proceeding with local anesthetic only.

Ultrasound-guided access into common femoral artery or radial artery will be obtained. An intra-arterial sheath will be placed. Through this sheath a diagnostic catheter will be used to perform pelvic angiography. Additionally, a cone beam CT angiogram may be performed. Based on these images and CT angiography obtained before the procedure, a microcatheter will be fluoroscopically guided into the prostatic artery. HydroPearl® microspheres (ranging from 75-400um based on the operator's discretion) will then be injected under fluoroscopic guidance to prevent reflux and non-target embolization. Injection will continue until there is stasis. The catheter will then be guided into the contralateral prostatic artery and repeat embolization will be performed until stasis. If necessary, extraprostatic arterial anastomoses will be embolized with a coil to protect against non-target embolization. The catheter and sheath will then be removed and hemostasis will be achieved with compression or an intra-arterial closure device. The subject subsequently will be discharged home the same day or the following day.

It is anticipated that less than 4 milliliters of HydroPearl® microspheres will be required for bilateral embolization. The size of the bead (75- 400 μ m) will be dependent on the operator's determination of what is most appropriate based on the size of the prostate and the prostatic vessels. The range in size of particles will allow the operators to discern the safest, most effective size for the vessels targeted. Embolic size will be based on the overall size of the prostate, size of the

target vessels, and likelihood of non-target embolization. For example, depending on how far the catheter can be advanced, smaller particles can be safely used to induce ischemia in the target tissue. This concept is utilized routinely within embolization procedures are commonly performed.

4.1.3 Method for Assigning Subject to Treatment Groups

All subjects will receive the intervention.

4.1.4 Prior and Concomitant Therapy

The subjects will be required to have been on medical therapy for BPH for at least six months prior to undergoing PAE. Such medications include alpha blockers, 5-ARIs or combination therapy. The medication usage will be stopped by the 3 month visit in order to allow an adequate washout period for 5-ARI's prior to the 6 –month visit.

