2.3 Outcome Variable

2.3.1 Primary Study Outcome Variable

Reduction in IPSS at 6-month follow-up.

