4.1.10 Visit 5 - 3 Month Follow-Up

Subjects will return 90 +/- 14 days after PAE procedure to complete IPSS, and QOL questionnaires; to have Qmax and PVR measured; medication history questionnaires will be completed; and subjects will be evaluated for possible adverse events. It will be recorded if subjects are unable to hold medications at this time due to residual urinary symptoms. If an AE is suspected based on change in pain scores or functionality, an appropriate work-up will be performed.

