4.1.11 Visit 6 - 6 Month Follow-Up

Subjects will return 180 +/- 14 days after PAE procedure to complete IPSS with QOL and medication history questionnaires and to have Qmax and PVR measured. The subjects will be evaluated for possible adverse events. If an AE is suspected based on change in pain scores or functionality, an appropriate work-up will be performed.

An MRI of the prostate will be acquired.

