8.3 Data Analysis Plans

A patient will be considered an evaluable study subject evaluable for data analysis per the following criteria, a written informed consent was obtained, he meets the inclusion and exclusion criteria, and received the PAE study procedure. All subjects with 12-month follow-up data will be included for analysis even if some follow up data is incomplete. Every attempt will be made to ensure that there is as

little missing data as possible including reminder phone calls and follow-up phone calls, if a subject misses a visit.

The primary aim is to demonstrate non-inferiority of PAE compared to medication with respect to the outcome measure IPSS. We assumed a non-inferiority margin of 10%, in line with the FDA's recommendations, since similar prior non-inferiority trials were unavailable. The null hypothesis states that in the target population mean IPSS is at least 10% greater at 6 months post-treatment than at baseline (pre-treatment). The alternative hypothesis will be that the mean IPSS at 6 months is less than or equal to 10% greater than the mean IPSS at screening.

To address this hypothesis we will implement a random effects linear model, modeling IPSS score as a function of time and the indicator of whether medication had stopped by the time of the 3-month follow-up. We will include an R-side compound symmetric random effect to account for patient-level correlation. We will compute the predicted mean and standard deviation(SD) of IPSS at screening and 6 months; the difference of the predicted mean IPSS score, defined as the mean IPSS at 6 months minus the mean IPSS at screening; and the SD of this difference. Point estimates of these values will be reported along with 95% confidence intervals for the mean difference.

A non-inferiority p-value <0.05 testing whether the difference in the predicted mean at screening is at least 10% greater than the predicted mean of IPSS at screening will be considered evidence against the null hypothesis of inferiority of PAE, compared to treatment. A non-inferiority p-value >0.05 will be considered inconclusive evidence against inferiority.

As a sensitivity analysis for the primary aim, we will repeat the same model outlined above after removing patients from the analysis who were still taking medications at the 3-month follow-up. Point estimates, confidence intervals, and p-values will be compared against those obtained in the primary analysis.

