12.0 APPENDICES

12.1 International Prostate Symptom Score (IPSS)

International Prostate Symptom Score (I-PSS)

Patient Name: _____ Date of birth: _____ Date completed _____

In the past month:	Not at All	Less than 1 in 5 Times	Less than Half the Time	About Half the Time	More than Half the Time	Almost Always	Your score
1. Incomplete Emptying How often have you had the sensation of not emptying your bladder?	0	1	2	3	4	5	
2. Frequency How often have you had to urinate less than every two hours?	0	1	2	3	4	5	
3. Intermittency How often have you found you stopped and started again several times when you urinated?	0	1	2	3	4	5	
4. Urgency How often have you found it difficult to postpone urination?	0	1	2	3	4	5	
5. Weak Stream How often have you had a weak urinary stream?	0	1	2	3	4	5	
6. Straining How often have you had to strain to start urination?	0	1	2	3	4	5	
	None	1 Time	2 Times	3 Times	4 Times	5 Times	
7. Nocturia How many times did you typically get up at night to urinate?	0	1	2	3	4	5	
Total I-PSS Score							

Score: 1-7: *Mild*8-19: *Moderate*20-35: *Severe*

Quality of Life Due to Urinary Symptoms	Delighted	Pleased	Mostly Satisfied	Mixed	Mostly Dissatisfied	Unhappy	Terrible
If you were to spend the rest of your life with your urinary condition just the way it is now, how would you feel about that?	0	1	2	3	4	5	6

About the I-PSS

The International Prostate Symptom Score (I-PSS) is based on the answers to seven questions concerning urinary symptoms and one question concerning quality of life. Each question concerning urinary symptoms allows the patient to choose one out of six answers indicating increasing severity of the particular symptom. The answers are assigned points from 0 to 5. The total score can therefore range from 0 to 35 (asymptomatic to very symptomatic).

The questions refer to the following urinary symptoms:

Questions	Symptom
1	Incomplete emptying
2	Frequency
3	Intermittency
4	Urgency
5	Weak Stream
6	Straining
7	Nocturia

Question eight refers to the patient's perceived quality of life.

The first seven questions of the I-PSS are identical to the questions appearing on the American Urological Association (AUA) Symptom Index which currently categorizes symptoms as follows:

Mild (symptom score less than or equal to 7)
Moderate (symptom score range 8-19)
Severe (symptom score range 20-35)

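### The off-drug interval before the 6-month IPSS is neither stated nor controlled, and both planned analyses use medication status at month 3 only

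*Combined protocol and SAP*

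**What the plan says.** All references are to the combined protocol and SAP.

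- **Stop rule (4.1.4).** "The medication usage will be stopped by the 3 month visit in order to allow an adequate washout period for 5-ARI's". The purpose is washout before the 6-month visit. No number of days is given.
- **Visit 5 (4.1.10).** "Subjects will return 90 +/- 14 days after PAE procedure". For men who cannot stop: "It will be recorded if subjects are unable to hold medications at this time due to residual urinary symptoms".
- **Visit 6 (4.1.11).** "Subjects will return 180 +/- 14 days after PAE procedure". IPSS with QoL, Qmax and PVR are taken here, and a medication history questionnaire is completed.
- **Primary outcome (2.3.1).** "Reduction in IPSS at 6-month follow-up".
- **IPSS recall (Appendix 12.1).** The symptom questions are headed "In the past month".
- **Primary model (8.3).** A random effects model, "modeling IPSS score as a function of time and the indicator of whether medication had stopped by the time of the 3-month follow-up".
- **Sensitivity analysis (8.3).** The same model after "removing patients from the analysis who were still taking medications at the 3-month follow-up".

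Both visits are timed from the procedure. No section sets a minimum interval between them or a minimum time from last dose to Visit 6, and neither analysis uses time since last dose or medication status at Visit 6.

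**The concern.** The primary comparison sets IPSS on medication at screening against IPSS at 6 months, when the effect is meant to be that of PAE without the drug. Section 4.1.4 recognises that this needs a washout, but leaves its length to the spacing of two visits that each move by 14 days either way.

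Any drug effect still present at Visit 6 lowers the 6-month score and so pushes towards non-inferiority of PAE. The QoL, Qmax and PVR readings at Visit 6 share the same off-drug interval. The planned analyses cannot show whether this has happened, because they classify men by status at month 3, about three months before the primary score is taken. A man who stops late and is scored early looks the same as one who stopped soon after the procedure. So does a man who had stopped at month 3 and has since resumed.

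**Working it through.** The plan states no washout length, so there is no figure of its own to reproduce. The check is calendar arithmetic on the windows, followed by tracing different men through the two analyses. The power figure in 8.2 is not affected.

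**Windows (4.1.10, 4.1.11)**
- Visit 5: 90 − 14 = day 76 to 90 + 14 = day 104.
- Visit 6: 180 − 14 = day 166 to 180 + 14 = day 194.

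**Interval for a man who stops at Visit 5**
- Shortest: 166 − 104 = 62 days.
- Nominal: 180 − 90 = 90 days.
- Longest: 194 − 76 = 118 days.
- Largest shortfall against nominal: (90 − 62)/90 = 31%.

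A man who stops before Visit 5 has a longer interval.

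**Allowing for IPSS recall (one month taken as 30 days)**
- Shortest: recall begins 62 − 30 = 32 days after the last dose.
- Nominal: 90 − 30 = 60 days.

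The like-for-like comparison is 32 with 60, not 32 with 90.

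**How often short intervals might arise.** Assume, for illustration only, that each visit falls evenly over its 29 permitted days, that the two are independent, and that the man stops at Visit 5. There are 29 × 29 = 841 date pairs.
- Interval under 70 days: 1 + 2 + … + 8 = 36 pairs, 36/841 = 4%.
- Interval under 90 days: 1 + 2 + … + 28 = 406 pairs, 406/841 = 48%.

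The extreme is uncommon, but falling somewhat short of nominal is not.

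**What depends on the unstated washout W, for men who stop at Visit 5**
- W of 62 days or less: the windows do no harm.
- W above 62 and up to 90 days: nominal timing is enough, but some permitted visit dates fall short.
- W above 90 days: nominal timing falls short as well.

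**How 8.3 treats each man**
- Stopped well before Visit 5 and stayed off: counted as stopped, kept in both analyses, appropriately.
- Stopped at Visit 5 on day 104, scored on day 166: counted as stopped, kept in both.
- Stopped by month 3, back on medication by Visit 6: counted as stopped, kept in both.
- Never stopped: flagged in the primary model, removed in the sensitivity analysis.

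The gap is in the second and third rows.

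**Size on the mean.** Bias in the mean = residual effect per affected man × fraction affected. Neither term is in the documents. As an illustration, assume 1 to 2 IPSS points per affected man and a baseline mean of 15 to 20, so that the 10% margin is 1.5 to 2.0 points.
- 10% of men affected: 0.1 to 0.2 points, or 5% (0.1/2.0) to 13% (0.2/1.5) of the margin.
- 25% affected: 0.25 to 0.5 points, or 13% (0.25/2.0) to 33% (0.5/1.5) of the margin.

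**The case against.** The strongest objection is that no standard in the documents is breached. Section 4.1.4 gives no number of days, so 90 is only what the nominal visits imply. It also makes Visit 5 the latest planned stop, not the usual one. This stands: the documents do not show that 62 days is too short.

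A reader might go further and infer that residual drug effect will be credited to PAE, by an amount comparable with the margin. The documents do not support that. They give no residual effect at any interval, and one man's effect cannot be set against a margin on the mean. The windows are symmetric around 90 days, and the washout rationale concerns 5-ARIs, whereas section 3.1.4 also admits men taking alpha blockers alone. The number at risk is unknown and smaller than the whole sample.

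Other points have partial force.

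- Men who cannot stop have an interval of zero, a more direct route to the same bias. That is true, but the indicator and the sensitivity analysis partly address it. They do nothing for men counted as stopped.
- A man who takes his last dose on the day of Visit 5 might be coded as still on medication and so be removed. The text does not settle this, but a man who stops a day or two earlier is plainly coded as stopped and gains only that day or two.
- The medication history form may already record a last-dose date. It is not reproduced (Appendix 12.2 shows only the adverse event form), so this can be neither confirmed nor ruled out. Section 8.3 makes no use of such a date in any case.
- IPSS is repeated at 12 months, at the earliest on day 360 − 14 = 346, which is 346 − 104 = 242 days after a day-104 stop. That helps in judging persistence, but it is not the primary endpoint, and the table in 4.3 schedules no medication history at that visit.
- Sections 4.1.1 and 8.1 place the MRI after the 6-month visit, so the 62-day figure is not established for prostate volume.

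**Conclusion.** The point holds as a gap in specification and analysis. The plan relies on a washout whose length it does not state. Its windows let the off-drug interval at the primary assessment range from 62 to 118 days for a man who stops at Visit 5, and neither planned analysis distinguishes a short interval, or resumed medication, from a full one. If there is any residual or resumed drug effect, its direction is known: it favours non-inferiority.

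Its size cannot be derived from the documents and is probably small on the mean. The 62-day figure is the extreme corner of two windows, and the effect sizes, affected fractions and baseline means used above are assumptions. The case for acting is that the remedy is cheap and that a last-dose date not recorded at the time may be hard to recover.

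A reader might also infer that Visit 6 should be barred until 90 days after the last dose. The documents do not support this. It would impose a washout length they never state, and it would leave a man who stops on day 104 a single permitted day (104 + 90 = 194).

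**What to change.** 1. **Reconcile 4.1.4 with 4.1.10 and 4.1.11.** The sponsor should state the off-drug interval before Visit 6 that the design relies on. This review does not propose what it should be.
2. **Capture the date.** Confirm that the medication history forms at Visits 5 and 6 record the last-dose date of each BPH medication and whether any is in use at that visit. Add the field if they do not.
3. **Extend the sensitivity analysis in 8.3.** Besides men still on medication at month 3, exclude men who are on medication at Visit 6 or whose time since last dose at Visit 6 is shorter than the stated interval. The nominal 90 days between visits could serve as an example, as an analysis cut-off only. Report how many men are excluded for each reason.

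The medication rule, the Visit 6 window and the primary model stay as they are.

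**Cost.** At most one date field, with no added visit or procedure. The real downside is a smaller sensitivity set. On the even-spread illustration, a 90-day cut-off would remove about 48% of men who stop at Visit 5, though fewer of those who stop earlier. Section 8.2's 20% dropout leaves 30 × 0.8 = 24 pairs, so the result would be imprecise and should be read for its point estimate and interval beside the primary result.

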4.1.5 Enrollment/Recruitment

Subjects will be recruited from the urology and vascular & interventional radiology (IR) clinics across three (3) sites.

4.1.6 Screening Visit (Visit 1)

If a patient qualifies to be a subject in the study based on the inclusion and exclusion criteria listed in section 3.1 and 3.2, the study coordinator will be notified. The coordinator will review the study with the patient and obtain written informed consent. Once the subject is enrolled in the study, he will be seen by one of the co-investigators in either the IR or Urology clinics at one of the study sites. The procedure will be again described to the patient and any questions will be answered. International Prostate Symptoms Survey (IPSS) with Quality of Life (QOL) questionnaires and Qmax and PVR measurements will be obtained if not completed in the prior 3 months during the pre-study work-up. Study specific questionnaires to assess medication usage will also be completed. A MRI of the pelvis with and without contrast will be ordered and obtained prior to visit 2 for baseline evaluation of the prostate unless the patient has one from the prior 6 months. If the patient had a contrast enhanced MRI of the pelvis within the past 6 months, this MRI will be used.

4.1.7 Visit 2 - PAE Procedure

PAE procedure will be performed as described in part 4.1.2 above within 8 weeks of Visit 1. Subjects will be given a pager number to reach a physician (24 hours a day) to report any adverse symptoms and receive medical advice.

Patients will be asked medication history questionnaire at this visit prior to the procedure.

4.1.8 Visit 3 -1 Day Follow-up

Subjects will be seen in clinic or contacted by phone or by teleconference, per the subject's preference, the day following PAE procedure (+3 days). As most

complications of the procedure will be evident within this time, this visit is to evaluate for early AEs. If an AE is suspected based on change in pain scores or functionality, an appropriate work-up will be performed which may include MRI or CT.

4.1.9 Visit 4 -1 Week Follow-up

Subjects will be seen in clinic or contacted by phone or by teleconference, per the subject's preference, one week following PAE procedure (+5 days). As most complications of the procedure will be evident within this time, this visit is to evaluate for early AEs. If an AE is suspected based on change in pain scores or functionality, an appropriate work-up will be performed which may include MRI or CT.

4.1.10 Visit 5 - 3 Month Follow-Up

Subjects will return 90 +/- 14 days after PAE procedure to complete IPSS, and QOL questionnaires; to have Qmax and PVR measured; medication history questionnaires will be completed; and subjects will be evaluated for possible adverse events. It will be recorded if subjects are unable to hold medications at this time due to residual urinary symptoms. If an AE is suspected based on change in pain scores or functionality, an appropriate work-up will be performed.

4.1.11 Visit 6 - 6 Month Follow-Up

Subjects will return 180 +/- 14 days after PAE procedure to complete IPSS with QOL and medication history questionnaires and to have Qmax and PVR measured. The subjects will be evaluated for possible adverse events. If an AE is suspected based on change in pain scores or functionality, an appropriate work-up will be performed.

An MRI of the prostate will be acquired.

4.1.12 Visit 7– 12 month follow-up for all subjects

Subjects will return 360 days +/- 14 days after PAE to complete IPSS and QOL questionnaires and to have Qmax and PVR measured.

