4.1.13 Subject Compliance Monitoring

Study coordinators and physicians will inquire of the subjects to determine if they have escalated any current or initiated any new conservative therapies during the follow-up period.

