4.2.2 Effectiveness Assessments

Technical success will be defined as bilateral prostatic artery embolization. This will be determined during the procedure. Clinical success will be defined as an IPSS score reported at the 6-month visit that is equal to or less than the pre-PAE baseline score. The size of the prostate will be measured by MRI at 6-month follow-up visit. IPSS, QoL, PVR and Qmax will be measured at 3, 6 and 12-month follow-ups.

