4.3 Time and Events Table

	Visit 1 (Screening)	Visit 2 (Procedure)	Visit 3 (1 Day)	Visit 4 (1 week)	Visit 5 (3 month)	Visit 6 (6 Month)	Visit 7 (12 month)
Informed Consent	X						
MRI	X					X	
PAE procedure		X					
IPSS w/QOL	X				X	X	X
Qmax	X				X	X	X
PVR	X				X	X	X
Medication History Questionnaire	X	X			X	X	
AE Assessment			X	X	X	X	

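### The 12-month visit schedules neither a medication history nor an adverse event assessment, so 12-month scores cannot be reliably read by medication status

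*Combined protocol and SAP*

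**What the plan says.** Section 4.1.12 sets out the 12-month visit in full: "Subjects will return 360 days +/- 14 days after PAE to complete IPSS and QOL questionnaires and to have Qmax and PVR measured". The visit six months before it, in 4.1.11, is wider. There the men "complete IPSS with QOL and medication history questionnaires and to have Qmax and PVR measured", and they are also evaluated for adverse events.

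The Time and Events Table (4.3) matches the text. The row "Medication History Questionnaire" is marked at Visits 1, 2, 5 and 6. The row "AE Assessment" is marked at Visits 3, 4, 5 and 6. Neither is marked at Visit 7.

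Section 4.2.2, on effectiveness, gives the 12-month scores the same standing as the others: "IPSS, QoL, PVR and Qmax will be measured at 3, 6 and 12-month follow-ups". Section 8.3 mentions them in its rule on who is analysed: "All subjects with 12-month follow-up data will be included for analysis".

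Two other places bear on medication. In 4.1.13, coordinators and physicians ask the men, to "determine if they have escalated any current or initiated any new conservative therapies during the follow-up period". In 8.3, the IPSS model contains time and one medication term: whether the man had stopped his drugs by the 3-month visit.

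**The concern.** The trial asks whether embolization can take the place of BPH medication. An IPSS answers that only if the reader knows whether the man was on medication when he gave it. The plan recognises this earlier in follow-up: 4.1.10 records men who cannot stay off their drugs at 3 months, and 4.1.11 repeats the medication questionnaire at 6 months.

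At 12 months that information is not scheduled, yet these are the only scores planned beyond 6 months. Men who restart are likely to be those whose symptoms came back, and the drug would then lower their score. A good 12-month mean could reflect embolization, resumed medication or both, and the scheduled data would not separate them. Harms that first appear after the 6-month visit likewise have no planned point at which anyone asks about them.

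**Working it through.** **The plan's own figure.** The documents give no figure for the 12-month visit. The one stated figure nearby is the 81.2% power in 8.2, so I checked whether the gap touches it.

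- Inputs from 8.2: SD 5.7 at both times, correlation 0.65, 30 pairs with 20% dropout, alpha 0.025 (taken as one-sided), decreases of 9.23 (embolization) and 6.6 (medication), margin 10%.
- SD of the difference = 5.7 × √(2 × (1 − 0.65)) = 4.769.
- Completers = 30 × 0.80 = 24.
- Expected difference = 9.23 − 6.6 = 2.63. With the margin read as 10% of that, the distance is 2.63 + 0.263 = 2.893.
- Paired t-test power (noncentral t) = 81.22%, against 81.2% stated.

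This reading of the margin is the one that reproduces the figure; whether it fits 8.3 is a separate matter. No input comes from Visit 7, so the gap leaves the power unchanged.

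**What is collected at each follow-up from 3 months (4.1.10 to 4.1.12, and 4.3).**

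| Item | 3 months | 6 months | 12 months |
|---|---|---|---|
| IPSS, QoL, Qmax, PVR | yes | yes | yes |
| Medication questionnaire | yes | yes | no |
| AE assessment | yes | yes | no |

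Text and table agree, so the omission is not an effect of a table broken in extraction.

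**What the model knows about medication.** The term in 8.3 is fixed at 3 months. The plan does not say which visits enter the model. If 12-month scores do, a man who stopped by month 3 and restarted at month 9 is still coded as stopped, and no scheduled form would show otherwise.

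**What the AE form could recover.** The questionnaire in Appendix 12.2 asks about the past month. Visits 6 and 7 are nominally 360 − 180 = 180 days apart. With a month taken as 30 days, the form as worded would leave 180 − 30 = 150 days uncovered even if it were used at Visit 7.

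**Illustration of size.** Let p be the proportion back on medication at 12 months and 6.6 the medication effect quoted in 8.2. If each man who resumes gains all of it, the mean looks better than off drug by p × 6.6:

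- p = 10% (3 of 30 men): 0.10 × 6.6 = 0.66 points
- p = 20% (6 of 30): 0.20 × 6.6 = 1.32 points
- p = 30% (9 of 30): 0.30 × 6.6 = 1.98 points

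Both p and the full additive effect after embolization are assumptions. The documents give no resumption rate.

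**The case against.** The strongest reply is that nothing is decided at 12 months. The primary outcome is "Reduction in IPSS at 6-month follow-up", clinical success in 4.2.2 is judged at 6 months, the other dated outcomes in 2.3.2 are at 6 months, and the AE outcome is at 3 months. The contrast in 8.3 is 6 months minus screening. All of this stands. It confines the point to the interpretation of 12-month data.

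Three stronger readings are tempting, and the documents do not support them.

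- *A man back on drugs would be counted as a lasting success of embolization.* No rule does this. There is no 12-month endpoint, success definition or durability claim, and the 12-month phrase in 8.3 concerns which subjects are included. The accurate statement is that his score could not be told apart from a lasting effect.
- *Medication use and late AEs are not collected at all.* Section 4.1.13 requires an inquiry during follow-up, which includes the 12-month visit. Section 9.3.1 says all AEs will be recorded, 6.3.1 requires reporting of unanticipated device effects without a visit limit, and the men have numbers to call. What remains is that the inquiry has no visit, form or analysis role, and that a man resuming his former drug is neither clearly escalating nor clearly starting something new. For AEs, capture after 6 months depends on spontaneous report.
- *The distortion is as large as the non-inferiority margin.* That margin applies to 6 months against screening, not to a 12-month score, and 8.3 sets it as a percentage of a screening mean that the documents do not give. Even at an assumed screening mean of 15 to 20 (margin 1.5 to 2.0), the illustration reaches it only at 1.5 / 6.6 = 22.7% to 2.0 / 6.6 = 30.3% resumption. The comparison should not be made.

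A last objection concerns the remedy. Reporting only the men off medication would select those in whom embolization probably worked, and so flatter it. That is right, and the fix below allows for it.

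**Conclusion.** The point holds in a limited form. Followed exactly, the plan yields 12-month IPSS, QoL, Qmax and PVR that cannot be reliably interpreted by medication status, and no scheduled capture of AEs between months 6 and 12. Both conclusions rest on 4.1.12 and 4.3 alone and need no assumption.

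The size is not known. The 0.66 to 1.98 points is an illustration that depends on an assumed 10-30% resumption and an assumed full 6.6-point gain in each man who resumes. A smaller gain after embolization would shrink it in proportion.

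The 6-month analysis stands as it is: its medication term is collected at 3 months, and medication is asked again at 6 months. This is a worthwhile, inexpensive correction to data collection. It does not threaten the primary result.

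**What to change.** 1. Add the existing Medication History Questionnaire and an AE assessment to Visit 7, in both 4.1.12 and the 4.3 table.
2. Word the AE recall at that visit to cover the whole time since the 6-month visit. The Appendix 12.2 form unchanged would miss most of it.
3. State in 8.3 how 12-month data will be reported: IPSS for all men, together with the proportion back on BPH medication. Show results by current medication status only as description, with a note that men off drug are a selected group.
4. State in 8.3 whether 12-month scores enter the IPSS model.

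The cost is a small amendment with IRB approval and a few more minutes per man at a visit that already takes place. Sample size and power do not change.
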